7.3 COLLECTION OF DATA AND STUDY MATERIALS

- Dendrite database
- Patient questionnaire

7.4 DATA STORAGE AND SECURITY

- All anonymous patient data will be stored on Dendrite maintained by the CI with oversight from the sponsor.
- The questionnaires will be send by the database Dendrite directly to the participants. Research nurses will call the participant in case of not completion.

7.5 ARCHIVING, PRESERVATION AND CURATION

Archiving will be authorised by the Sponsor following submission of the end of study declaration. Upon completion of the study, study documents will be archived for a minimum of 5 years as per the participating Trust's Research Archiving SOP. Once the archiving retention period has been reached, the Sponsor will liaise with the CI regarding destruction.

7.6 DATA SHARING

Requests for data sharing can be made after publication of the primary results paper. Requests should be made to the Chief Investigator in the first instance. Requesters will be asked to complete an application form detailing specific requirements, rationale, and proposed usage. The CI and study sponsor (including the sponsor's Research Governance Manager (or deputy), the Information Governance Team, Calidcott Guardian, IM&T Security Officer and the researcher funder, as appropriate) will review all requests.

Consideration will be given to:

- 1. The viability and suitability of the request
- 2. Appropriate steps have been taken to minimise the risk of identifying participants
- 3. Data security policies and procedures of recipient organisation (including country if abroad) and other regulatory requirements are applicable
- 4. The credentials of the requestor

Where access to requested data is granted, requesters organisation must sign a data sharing agreement before they can access any data.

Subject to appropriate data sharing agreements, individual participant's data that underlie the results will be made available (after de-identification) on a controlled access basis. Requested data

will be made available, along with supporting documentation (e.g., data dictionary) on a secure server or through other secure data transfer method.

8 ETHICAL AND REGULATORY COMPLIANCE

8.1 ETHICS AND HRA APPROVAL

The Chief Investigator will obtained approval from the Health Research Authority (HRA) and Research Ethics Committee (REC). The Investigator will ensure that this study is conducted in full conformity with relevant regulations and with the UK Policy Framework for Health and Social Care Research (2017), which have their basis in the Declaration of Helsinki.

8.2 INDEMNITY

This is an NHS-sponsored research study. If an individual suffers negligent harm as a result of participating in the study, NHS indemnity covers NHS staff and those people responsible for conducting the trial who have honorary contracts with the relevant NHS Trust. In the case of non-negligent harm, the NHS is unable to agree in advance to pay compensation, but an *ex-gratia* payment may be considered in the event of a claim.

8.3 SPONSOR

UHP will act as the main sponsor for this study assuming overall responsibility for the initiation and management of the trial. Delegated responsibilities maybe assigned to other relevant parties taking part in this study and appropriately documented.

8.4 FUNDING

Funding for the use of the Dendrite Database, institutional set up and data collection will be obtained from Penumbra Inc. Data will be collected at all centres by research nurses with appropriate funding. Statistics analysis will be performed the University of Plymouth Statistics team.

8.5 MONITORING

The study will be subject to monitoring by UHP under their remit as sponsor to ensure adherence to the UK Policy Framework for Health and Social Care Research (2017). All UHP studies will be initially monitored before Green Light being given. The subsequent level of monitoring will be determined by a risk assessment, or on a for cause basis. The study may also be audited / inspected by regulatory bodies to ensure compliance with national regulations.

9 STUDY MANAGEMENT

The day-to-day management of the study will be co-ordinated through [name].

10 PUBLICATION POLICY

Final results of the study will be disseminated via presentations at appropriate scientific meetings, and publication in appropriate peer-reviewed journals. Authorship will involve named individuals involved in study design and manuscript preparation according to the guidelines given by the ICMJE (International Committee of Medical Journal Editors).

12 APPENDICIES

12.1 APPENDIX 1 – SCHEDULE OF EVENTS

For ALL Participants

Assessments	Visits						
	PERT referral	Discharge	30 (± 7) days post op	90 (± 14) days post op	6 (± 1) months post op		
Informed consent	X						
Demographics	Х						
Admission observations	Х						
Biochemistry (WBC, RBC, CRP, GFR, BNP)	X						
PESI score	X						
CT findings	Х						
RV/LV ratio	Х						
Pulmonary arterial pressure	Х						
PERT team assessment	Х						
Further procedures		X					
Length of stay		Х					
Mortality		X	Χ	Х	X		

	Visits					
Assessments	PERT referral	Discharge	30 (± 7) days post op	90 (± 14) days post op	6 (± 1) months post op	
Readmission			Х	X		
Questionnaires						
PEmb-QoL			Х	X	X	
ED-5D-5L			Х	X	X	
Borg Scale			Х	X	X	

Only for CAVT treatment

Accomments	Visits						
Assessments	PERT referral	Day 1 post op	Day 2 post op	Day 3 post op	Day 5 post op	Discharge	
Procedure outcome	X						
Thrombectomy time	Х						
Observations		Х	Х	Х	Х		
Temperature		Х	Х	Х	Х		
Blood Pressure		Х	Х	Х	X		
Pulse		Х	Х	Х	X		
Oxygen saturation		Х	Х	Х	Х		
Glasgow Coma Scale		Х	Х	Х	Х		
Biochemistry (WBC, RBC, CRP, GFR, BNP)		Х		Х	Х		
Echocardiogram with LV/RV ratio			Х				
Further procedures						Χ	
Length of Stay						Χ	
Mortality						X	
Readmission							
Questionnaires							
PEmb-QoL							

Accesaments	Visits					
Assessments	PERT referral	Day 1 post op	Day 2 post op	Day 3 post op	Day 5 post op	Discharge
ED-5D-5L						
Borg Scale						

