Dendrite	Dendrite clinical systems, electronic research database
Section 251	The purpose of section 251 support is to give the data controller a legal means of providing access to confidential patient information without consent.
SOP	Standard Operating Procedure
SPSS	Statistical Product and Service Solutions (statistical software suite)
UHP	University Hospitals Plymouth NHS Trust
USS	UltraSound Scan
WBC	White Blood Cell

KEY WORDS:

Pulmonary embolism, Thrombectomy.

STUDY SUMMARY

Study Title TiPE

Study Design Prospective observational study to evaluate the use of Computer aided

vacuum thrombectomy (CAVT) within the context of intermediate and

high-risk PE.

Study Participants Patients presenting with intermediate or high-risk PE (as defined by

European Society of Cardiology (ESC) guidelines1) at one of the

participating hospitals.

Eligibility Criteria Study Site Criteria:

1. Availability of 16Fr Penumbra Flash

2. Operational PE Response team

3. Operator experience treating a minimum of 2 previous PE's and experience with Penumbra indigo systems (defined as 3 cases).

Inclusion Criteria Participants:

1. Clinical signs and symptoms consistent with acute PE with duration of 14 days or less

2. Patients who present with CT confirmed PE

3. Defined as intermediate or high-risk PE (according to ESC guidelines¹)

4. Date of CT imaging from within the two-year period

5. Patient is ≥ 18 years of age

6. Informed consent obtained

7. Evidence of cardiac dysfunction (Either biochemical or imaging features of RHS)

Exclusion Criteria:

- 1. Known serious, uncontrolled sensitivity to radiographic agents
- 2. CT not available to evaluate PE
- 3. Low Risk PE as defined by ESC guidelines¹
- 4. Current participation in another investigational drug or device study that may confound the results of this study. Studies requiring extended follow-up for products that were investigational but have since become commercially available are not considered investigational studies
- 5. Other medical, social, or psychological conditions that, in the opinion of the Investigator, precludes the patient from appropriate consent, could limit the patient's ability to participate in the study, including compliance with follow-up requirements, or that could impact the scientific integrity of the study

Planned Sample Size 2000 eligible patients and 200 thrombectomy patients

Follow-up Duration 6 months from date of PE or date of death, whichever is sooner

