2.2 SECONDARY OBJECTIVES

- 1. To identify factors that determine the decision to use thrombectomy within the PERT team
- 2. To evaluate the factors that predict outcome of CAVT
- 3. To evaluate the patient tolerance and experience in the form of patient related outcome measures (PROMS) of CAVT

- 4. To evaluate the effectiveness and risk profile of CAVT in high-risk patients, including effects of concurrent lytic therapy where given
- 5. To evaluate the effect of service design on PE CAVT rate and outcomes
- 6. To compare variability in provision of CAVT between hospitals and its effect on performance and outcomes.
- 7. To evaluate the relationship between severity and outcome in patients receiving CAVT
- 8. To determine imaging features that are associated with poor outcomes in patients undergoing CAVT
- 9. To determine the effectiveness of CAVT in relationship to the age of the thrombus
- 10. To evaluate the perceived dyspnoea at 30 days and 6 months after CAVT, and also in comparison to the non-intervened group
- 11. To evaluate Quality of life as assessed by EQ-5D-5L and PEmb-QoL at 30, 90 days and 6 months for all participants.
- 12. Incidence of device related SAE(s)
- 13. Evaluate the impact of the length of procedure time and the operator decided end point of CAVT, including technical success and its effect on outcomes
- 14. To evaluate the time to CAVT and its effect on outcomes and resource utilisation.

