5.2 REPORTING PROCEDURES

At each data collection (30 days, 90 days and 6 months from the thrombectomy) the investigator will determine whether adverse events about the device and procedure have occurred. Subjects participating in the study should be encouraged to report these AEs spontaneously or in response to general, non-directed questioning.

Relevant events will be collected from the signing of informed consent to the completion of the follow up 6 months post index procedure.

19/10/25; V1.0

Adverse Events

AEs will be recorded for the CAVT and relevant procedure only.

Any AEs related to the CAVT will also be reported to the company Penumbra and MHRA.

Please find in Appendix 3 expected adverse events of CAVT and relevant procedure.

Serious Adverse Events

Death due to any pre-existing conditions will not be reported as SAEs.

Serious adverse events will be recorded.

Only CAVT related SAEs will be reported to the Principle Investigator, the Chief Investigator and Sponsor within 24 hours of being aware of the event. An Independent Medical Reviewer for the SAEs will also be appointed and the opinion will be recorded along with the PI / CI opinion. A SAE form should be completed.

All CAVT related SAEs should be reported to the Name of REC and copied to the Sponsor, and Penumbra where in the opinion of the Chief / Principal Investigator and the Independent Medical Reviewer, the event was:

- 'related', i.e. resulted from the administration of any of the research procedures; and
- 'unexpected', i.e. an event that is not listed in the protocol as an expected occurrence

Reports of related and unexpected SAEs should be submitted within 15 days of the Chief / Principal Investigator becoming aware of the event, using the Non-CTIMP safety report to REC form for non-IMP studies.

Sponsor contact details for reporting SAEs

Please send SAE forms to: R&D Governance / R&D Office

[contact] (Mon to Fri 09.00 – 17.00)

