6.2 ANALYSIS

Patient demographic and clinical characteristics will be summarised using appropriate descriptive statistics. The primary outcome, change in LV/RV ratio before and at 48 hours post baseline will be summarised according to risk group and overall and will be assessed with a two-sided paired t-Test. Linear regression analysis will be used to identify factors, including severity, affecting the change in LV/RV ratio. Survival analysis will be used to model factors affecting mortality. Data will be analysed using R or Stata. An unblinded interim analysis at 100 patients will be performed at 6 month follow up with focus on the primary outcomes. No Stop/Go criteria will be applied as the PE response team decision to treat or not is not protocolised and the study is observational only. A detailed statistical analysis plan will be written with the University of Plymouth Medical Statistics group and finalised before database lock.

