7.1 DATA FLOW DIAGRAM

7.2 DESCRIPTION OF THE DATA

Sample data points will include the following for **ALL** patients:

Patient demographics

Age, Sex, Medical History, Cancer, Pregnancy, Time of first symptoms, presenting hospital, admission from location (e.g. Own Home/nursing home) transfer in, previous PE, Anticoagulation, Concurrent DVT and Position.

Admission / Diagnosis (at point of diagnosis of PE if not on admission)

Admission observations, Biochemistry including Temperature, BP, Pulse, oxygen saturations and GCS, biochemistry including: WCC, RBC, CRP, GFR and BNP and Troponin

CT findings (including Evidence of RHS parameters including IVC contrast reflux, Septal flattening, clot location, reporter grade)

Base line (Day of referral to PERT if not day of admission)

PESI score, , RV/LV ratio CT, RV/LV ratio USS. Presence of right atrial clot, PFO presence on Echocardiography, eligibility for thrombolysis (e.g. recent head trauma/ ischaemic stroke, previous ICH, Intracranial neoplasm, GI malignancy, GI haemorrhage in previous 21 days, Recent surgery, BP >185, active bleeding, infective endocarditis, Clotting abnormalities), If Thrombolysis given, including dose.

PER Team first assessment including date and time

PER Team initial decision outcome, date and time

PER Team review - Change Decision, date and time - and change in observations and Biochemistry PER Team review - Change Decision 2, date and time - and change in observations and Biochemistry

Discharge

Further procedures, length of stay, (including ICU, HDU, Ward), mortality, Place of discharge to. IVC filter insertion.

Follow up

Day 30 (± 7 days): All cause and PE related Mortality, Local readmission – Patient questionnaire: PEmb-QoL, EQ-5D-5L, Borg Scale

Day 90 (± 14 days): Mortality, Local readmission – Patient questionnaire: PEmb-QoL, EQ-5D-5L, Borg Scale

6 months (+/- 30 days): All cause and PE related Mortality – Patient questionnaire: PEmb-QoL, EQ-5D-5L, Borg Scale

Those undergoing CAVT will have the following additional data collected:

Procedural success and outcome. Procedural time, Access route, Aspiration device used, Separator used, Heparin given, including dose, Concurrent Lysis used, including dose. Thrombectomy time. Pulmonary arterial pressure at start, Pulmonary Arterial pressure at finish. Requiring further procedures, Length of stay, IVC filter insertion, readmission along with:

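### The follow-up schedule for all participants counts from an operation that about 90% of them do not have, so time zero is undefined for most of the cohort and contradicted elsewhere

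*Protocol*

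**What the plan says.** The protocol places the start of follow-up differently in different sections.

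- **Appendix 1 (12.1).** The table headed "For ALL Participants" has a PERT referral column, a discharge column and three follow-up columns. The first of these is "30 (± 7) days post op"; the 90-day and 6-month columns are also post-operative. Mortality, PEmb-QoL, the EQ-5D and the Borg scale are due at all three, and readmission at the first two.
- **Study summary.** Follow-up lasts "6 months from date of PE or date of death, whichever is sooner". The planned sample is "2000 eligible patients and 200 thrombectomy patients".
- **Section 7.2, data for all patients.** The entries begin "Day 30 (± 7 days): All cause and PE related Mortality" and continue with Day 90 and 6 months. No starting point is named.
- **Section 5.2.** "At each data collection (30 days, 90 days and 6 months from the thrombectomy" is the timing for adverse events of the device and procedure.
- **Section 2.2, secondary objective 10.** "To evaluate the perceived dyspnoea at 30 days and 6 months after CAVT, and also in comparison to the non-intervened group". The summary's version adds 90 days. The summary's objective 11 also compares quality of life with the non-intervention group; section 2.2 asks for it in all participants without naming a comparison.
- **Section 6.2.** "Survival analysis will be used to model factors affecting mortality", with no origin stated.

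**The concern.** A follow-up schedule has to tell a site when to contact each participant. For someone managed without CAVT, a post-operative day 30 does not exist. Sections 4.4 and 7.4 have the Dendrite platform send the questionnaires, so the database needs a trigger date. With none defined for these participants, 12 sites could start from CT diagnosis, referral, admission or discharge.

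This falls directly on the planned comparisons. Objective 10 times the CAVT patients from the procedure, and the comparison group cannot be timed that way. Differences in breathlessness or quality of life would then partly reflect time since the PE. The SAP can choose a time origin for mortality if dates are recorded, but it cannot move a questionnaire that has already been answered.

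Mortality raises a second question. CAVT patients must survive to the procedure. If deaths before it were counted with the untreated patients, CAVT would look better even with no effect.

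**Working it through.** **1. Share of the cohort without an operation.** Summary: 2000 − 200 = 1800, and 1800 / 2000 = 90%. Section 4.2 makes the CAVT patients a subset of the wider dataset, so the subtraction is proper. From the volumes in sections 4.1 and 6.1:

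- Eligible: 12 × 130 × 2 = 3120; at 70% consent, 2184.
- Thrombectomy: 12 × 13 × 2 = 312; at 70% consent, 218.
- From the rounded 3000 and 300: 2100 and 210.

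The stated 2000 and 200 are somewhat lower, which looks like rounding down. The share without an operation is 90% in each case (1 − 13/130 = 0.90).

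**2. The origins side by side.**

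| Place | Population | Origin |
|---|---|---|
| Appendix 1 | All participants | Operation |
| Summary, follow-up duration | All participants | Date of PE |
| Section 7.2, follow-up | All patients | None given |
| Section 5.2 | CAVT device and procedure events | Thrombectomy |

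The first three describe the same visits for the same people and disagree. The fourth concerns CAVT patients only and is coherent as it stands.

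**3. Size of the questionnaire shift.** It equals the interval from the comparator's origin to the procedure. The protocol does not give this interval, so I assume 0.5 to 7 days.

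| Interval | Share of ±7 days | Share of ±14 days | Share of ±30 days |
|---|---|---|---|
| 0.5 days | 7% | 4% | 2% |
| 2 days | 29% | 14% | 7% |
| 7 days | 100% | 50% | 23% |

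Short waits are absorbed by the windows. Only a wait of about a week fills the half-window at 30 days.

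**4. Mortality: which part of any bias comes from the clock?** All inputs here are assumptions and the true effect is null. Patients selected for CAVT who die first are counted as non-CAVT.

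*Step hazard.* 11% are selected and the wait W is exponential with mean w. The daily hazard is h for 3 days, then 0.15%, so S(t) = exp[−h·min(t,3) − 0.0015·max(t−3,0)].

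- CAVT from the operation: E[S(W) − S(W+30)] / E[S(W)]
- CAVT from referral: E[S(W) − S(30)] / E[S(W)]
- Non-CAVT from referral: {0.89[1 − S(30)] + 0.11·E[1 − S(W)]} / {1 − 0.11·E[S(W)]}

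30-day mortality ratio, CAVT to non-CAVT, by numerical integration:

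| Mean wait | h | Differing clocks | Both from referral |
|---|---|---|---|
| 0.5 d | 1% | 0.934 | 0.924 |
| 0.5 d | 2% | 0.902 | 0.895 |
| 1 d | 1% | 0.875 | 0.855 |
| 1 d | 2% | 0.816 | 0.802 |
| 2 d | 1% | 0.797 | 0.757 |
| 2 d | 2% | 0.701 | 0.673 |

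Putting both groups on one clock moves the ratio slightly further from 1. The distortion comes from requiring survival to CAVT, not from the column heading.

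*Weibull hazard.* 10% receive CAVT after a fixed gap g; 30-day mortality m is 5% to 20%; S(t) = exp[ln(1−m)·(t/30)^k]. Example with m = 10%, g = 1 day, k = 0.5 (front-loaded):

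- S(1) = 0.9809, S(31) = 0.8984, S(30) = 0.9000.
- CAVT from the operation: 1 − 0.8984/0.9809 = 0.0841. CAVT from PE: 1 − 0.9000/0.9809 = 0.0825.
- Share destined for CAVT: 0.1/0.9809 = 0.1019. Non-CAVT: [0.8981 × 0.1000 + 0.1019 × 0.0191]/0.9 = 0.1019.
- Ratios: 0.83 and 0.81.

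Over gaps of 0.5 to 7 days:

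| Hazard | Differing clocks | Both from PE |
|---|---|---|
| Constant (k = 1) | 0.98 to 1.00 | 0.75 to 0.98 |
| Front-loaded (k = 0.5) | 0.60 to 0.88 | 0.50 to 0.87 |

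**The case against.** The best defence is that this is a labelling slip. Both primary objectives concern CAVT patients, for whom a procedure clock is meaningful, and the RV/LV test is paired within patient. The named cross-group comparisons rest on questionnaires with wide windows. Section 6.2 leaves detail to a SAP, and section 7.2 records each PERT decision with date and time, so an analyst could set a sound origin later. Most of this stands: the primary analyses are untouched and the questionnaire shift is probably small. What does not stand is that the SAP can repair everything. The schedule governs when data are collected, and it gives no date for 90% of participants.

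A reader might go further and infer that the plan builds in immortal-time bias in favour of CAVT. The protocol does not support that. It states no rule for classifying patients who die before CAVT, and no explicit mortality contrast of CAVT with non-CAVT; section 6.2 only models factors affecting mortality. The risk is still not fanciful. The PERT decision can change on review (7.2), time to CAVT is itself an objective, deaths within 96 hours can be included by proxy consent (4.3), and the Outcomes section plans regression of outcomes on the PERT decision.

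Nor do several sections start at the date of PE. Only the summary does.

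**Conclusion.** The point holds as a defect in the stated schedule. The time origin for mortality, readmission and questionnaires is undefined for about 1,800 of 2000 participants, and Appendix 1, the summary and section 7.2 disagree. This rests on the documents alone.

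The consequence for the comparisons of dyspnoea and quality of life is a difference in assessment time, probably small if CAVT follows within a few days. The protocol does not give that interval.

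Immortal-time bias is conditional on how CAVT is later analysed, and its size depends on assumed waits and hazards. With no true effect, the 30-day mortality ratio runs from about 0.7 to 0.93 under the step hazard. For the differing clocks it is close to 1 under constant hazard, and lower when deaths are front-loaded and waits are long. Correcting the column heading would not by itself remove this bias.

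**What to change.** 1. Name one time zero that every participant has. PERT referral is the natural candidate, being already the baseline column of Appendix 1. Use it for the three follow-up columns of the all-participants schedule, the Dendrite questionnaire trigger and every comparison of CAVT with non-intervened patients, including objective 10 and the summary's objective 11.
2. Reconcile the summary's follow-up duration and section 7.2 with that origin.
3. Keep the procedure clock, and say so, for CAVT-only outcomes: the 48-hour and Day 1 to 5 data, the CAVT mortality and morbidity profile of primary objective 2, and the device and procedure events of section 5.2.
4. State that if CAVT enters the survival model or any mortality comparison, it will be a time-dependent exposure from the common origin, or a landmark analysis will be used.

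The cost is wording in three places, one sentence for the analysis and a database date field. For CAVT patients the questionnaire date moves earlier by the interval from referral to procedure. One contact can usually serve both clocks: the 30-day windows are days 23 to 37 from each origin, and they overlap for any interval up to 14 days. The protocol is version 1.0 with an empty amendment history, so the change is cheapest before questionnaires go out.
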